**Table 6-2 Criteria for dose interruption and re-initiation of crizanlizumab treatment for adverse drug reactions.**

Dose modifications for crizanlizumab	
Worst toxicity	
CTCAE a Grade (CTCAE version 5) during a cycle of therapy	
Investigations (Hematologic)	
Neutropenia (ANC)	
Grade 1 (ANC < LLN - 1.5 x 10  /L)	Recommendation: Maintain dose
Grade 2 (ANC < 1.5 x 10  /L-1.0 x 10  /L )	Recommendation: Maintain dose
Grade 3 (ANC < 1.5 x 10  /L-0.5 x 10  /L )	Mandatory: Interrupt dose until resolved to ≤ Grade 2 or next dose scheduled. If abnormality persists, permanently discontinue the subject from the study.
Grade 4 (ANC < 0.5 x 10  /L)	Mandatory: Permanently discontinue the subject from the study.
Febrile neutropenia (ANC < 1.0 x 10  /L, fever ≥ 38.3°C)	Mandatory: Interrupt dose until resolved or next dose schedule. If abnormality persists, permanently discontinue the subject from the study.
Trombocytopenia	
Grade 1 (PLT < LLN - 75 x 10  /L)	Recommendation: Maintain dose
Grade 2 (PLT < 75 - 50 x 10  /L)	Recommendation: Maintain dose
Grade 3 (PLT < 50 - 25 x 10  /L)	Recommendation: Interrupt dose until resolved to ≤ Grade 2 or next dose scheduled. If abnormality persists, permanently discontinue the subject from the study.
Grade 4 (PLT < 25 x 10  /L)	Mandatory: Permanently discontinue the subject from the study.
Investigations (Hepatic)	
Isolated Direct Bilirubin	
Grade 1 (>ULN - 1.5 x ULN if baseline was normal; > 1.0 - 1.5 x baseline if baseline was abnormal)	Recommendation: Continue study treatment

Grade 2 and 3 (>1.5 - 10.0 x ULN if baseline was normal; >1.5 - 10.0 x baseline if baseline was abnormal)	Recommendation: Interrupt study treatment. Monitor liver function tests (LFTs) b weekly, or more frequently if clinically indicated, until resolved to $\leq$ 1.5 x ULN or baseline. If resolved to $\leq$ Grade 1 or baseline, then continue study treatment.
Grade 4 (>10.0 x ULN if baseline was normal; >10.0 x baseline if baseline was abnormal)	Mandatory: Permanently discontinue from study treatment.
Isolated ALT elevation	
Grade 1 (> ULN - 3.0 x ULN)	Recommendation: Maintain dose
Grade 2 (> 3.0 - 5.0 x ULN)	Recommendation: Maintain dose. Repeat LFTs b as soon as possible, preferably within 48-72 hours from awareness of the abnormal results; if abnormal lab values are confirmed upon the repeat test, then monitor LFTs b weekly, or more frequently if clinically indicated, until resolved to $\leq$ 3.0 x ULN. If resolved, then continue with next dose scheduled.
Grade 3 (> 5.0 - 20.0 x ULN)	Recommendation: Interrupt dose. Repeat LFTs b as soon as possible, preferably within 48-72 hours from awareness of the abnormal results; monitor LFTs b weekly, or more frequently if clinically indicated, until resolved to $\leq$ 3.0 x ULN. If resolved, then continue with next dose scheduled
Grade 4 (> 20.0 x ULN)	Mandatory: Permanently discontinue the subject from the study.
Combined c elevations of ALT and bilirubin (direct [conjugated])	
For subjects with normal baseline ALT and direct bilirubin value: 
 
ALT > 3.0 x ULN combined with direct bilirubin > 2.0 x ULN without evidence of cholestasisc
 
 OR For subjects with elevated baseline ALT or direct bilirubin value: 
 
ALT > 2 x baseline AND direct bilirubin > 2.0 x baseline
 
	Mandatory: In the absence of cholestasis c (ALP < ULN), subject should be immediately discontinued from study treatment. Repeat LFTs b as soon as possible, preferably within 48 hours from awareness of the abnormal results, then with weekly monitoring of LFTs b , or more frequently if clinically indicated, until ALT, or bilirubin have resolved to baseline or stabilization over 4 weeks. Refer to Section 6.5.1.1 for additional follow-up evaluations as applicable.
Infections	

Grade 1	Recommendation: Maintain dose level
Grade 2	Recommendation: Maintain dose level
Grade 3	Mandatory: Interrupt dose until resolved. If resolved, then continue with next dose scheduled.
Grade 4	Mandatory: Permanently discontinue the subject from the study.
Infusion-related reactions	
Grade 1  Mild transient reaction; infusion interruption not indicated; intervention not indicated	
Recommendation:
 

Continue study treatment and increase monitoring of vital signs as medically indicated until the subject is deemed medically stable in the opinion of the investigator.

Consider slowing infusion rate.

Grade 2  Therapy or infusion interruption indicated but responds promptly to symptomatic treatment (e.g., antihistamines, NSAIDS, narcotics, IV fluids); prophylactic medications indicated for <=24 hrs	
Recommendation:
 

Temporarily interrupt infusion and increase monitoring of vital signs as medically indicated until the subject is deemed medically stable in the opinion of the investigator.

Administer appropriate medical therapy (e.g. analgesics such as paracetamol /acetaminophen or NSAIDs and anti-histamines), as per local institutional guidelines and clinical presentation.

Steroids should be used with caution unless clinically indicated (e.g. management of hypersensitivity/anaphylaxis).

If symptoms resolve, restart infusion per investigator discretion at a slower rate under continuous observation. Ensure a minimum of 1 hour observation period prior to restarting the infusion.

Before restarting, administer premedication (e.g. analgesics such as paracetamol/acetaminophen or NSAIDs and anti-histamines within 1 hour prior to dosing) as per local institutional guidelines for prophylaxis of infusion related reactions, including subsequent infusions.

In case of recurring infusion reactions despite premedication and prolonged infusion, consider discontinuation of study treatment.

Grade 3 and 4 Prolonged (e.g., not rapidly responsive to symptomatic medication and/or brief interruption of infusion); recurrence of symptoms following initial improvement; hospitalization indicated for clinical sequelae Life-threatening consequences; urgent intervention indicated
	
Mandatory:
 

• Permanently discontinue study treatment.

---	---

General Note: Decision for dosing is made on prior lab results, not those from labs performed on the day of infusion. If lab results are found to be abnormal, repeat (unscheduled) labs should be performed at least 1 week prior to scheduled dose in order to have results showing resolution of the abnormality before the scheduled dose is given.

a Common Terminology Criteria for Adverse Events (CTCAE Version 5.0)

b Core LFTs consist of ALT, AST, GGT, total bilirubin (fractionated [direct and indirect]), and alkaline phosphatase

c "Cholestasis" defined as ALP elevation ( $> 2.0 \times$  ULN and R value  $< 2$ ). Note: The R value is calculated by dividing the ALT by the ALP, using multiples of the ULN for both values. It denotes whether the relative pattern of ALT and/or ALP elevation is due to cholestatic (R  $\leq 2$ ), hepatocellular (R  $\geq 5$ ), or mixed (R  $> 2$  and  $< 5$ ) liver injury

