### **Infections**

Based on the mechanism of action and physiological role of P-selectin, crizanlizumab could potentially be associated with an increased infection risk.

Infection-related AEs (based on all preferred terms included in the system organ class "Infections") were reported in 55 (49.5%) patients in the safety pool. The most frequently reported infections were urinary tract infection (13 patients, 11.7%), upper respiratory tract infections (11 patients, 9.9%), pneumonia (5 patients, 4.5%) and sinusitis (4 patients, 3.6%). Most infections were low in severity (Grade 1 or 2). In the randomized SUSTAIN study, infection-related AEs were similar across the arms: 53.0% in the crizanlizumab 5 mg/kg and 53.2% in the placebo arm. In addition, there was no difference between the arms in the incidence of neutropenia or white blood cell counts.

In summary, no increased frequency or severity of infections has been observed in clinical studies with crizanlizumab so far, suggesting that crizanlizumab has no clinically relevant effect to induce or complicate infections in SCD patients. However, investigators are advised to monitor patients for signs/symptoms of infections.

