## **6.5 Dose modification**

If a subject does not tolerate the protocol-specified dosing schedule, dose interruptions are either recommended or mandated in order to allow subjects to continue the study treatment until the next scheduled dose. Dose reductions are not allowed.

If a subject experiences drug-induced toxicity, the subject should be closely monitored and a decision to continue or discontinue the subject from the study should be done at the next scheduled dose.

These dose interruptions are summarized in [Table 6-2](#). Deviations to mandatory dose interruptions are not allowed. Permanent treatment discontinuation is mandatory for specific events indicated as such in [Table 6-2](#).

Dose interruptions must be recorded in the Dosage Administration Record CRF. Every effort should be made to maintain the subject on the protocol-defined dosing schedule. In case of dose delay for any reason, the dose should be given as soon as possible. If that infusion visit occurs within  $\pm$  7 days of a protocol-scheduled visit, then the dose and all required assessments will be assigned to the nearest protocol-scheduled visit. However, if that infusion visit does not fall within  $\pm$  7 days of a protocol-scheduled visit, the dose and corresponding assessments will be documented as an unscheduled visit. At that point, every effort should be made to bring the subject's infusions back onto the protocol-defined schedule (within the  $\pm$  7 day window).. If a subject misses two consecutive doses of crizanlizumab due to ADR (i.e., an AE attributable to study drug), the subject should be discontinued from crizanlizumab. A subject with Grade 3 or 4 IRR will be permanently discontinued from crizanlizumab. A subject with a Grade 4 ADR will be permanently discontinued from the study.

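### Table 6-2 prints two action thresholds that contradict the rest of the protocol: the Grade 3 neutropenia band overlaps all of Grade 2, and the ALP bracket disagrees with footnote c and Section 6.5.1.1 (minor)

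*Protocol*

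**What the plan says.** Protocol Table 6-2, titled "Criteria for dose interruption and re-initiation of crizanlizumab treatment for adverse drug reactions", links CTCAE version 5 grades to dosing actions.

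- **Neutropenia, Grade 2:** "Grade 2 (ANC < 1.5 x 10 9 /L-1.0 x 10 9 /L", with a recommendation to maintain the dose.
- **Neutropenia, Grade 3:** "Grade 3 (ANC < 1.5 x 10 9 /L-0.5 x 10 9 /L", with a mandatory action: "Interrupt dose until resolved to ≤ Grade 2 or next dose scheduled". If the abnormality persists, the subject leaves the study permanently.
- **Neutropenia, Grade 4:** ANC below 0.5 x 10^9/L, mandatory permanent discontinuation.
- **Febrile neutropenia:** "Febrile neutropenia (ANC < 1.0 x 10 9 /L, fever ≥ 38.3°C", mandatory interruption.
- **Combined ALT and direct bilirubin elevation:** the mandatory action cell marks the word cholestasis with footnote c and then adds its own bracket: "ALP < ULN), subject should be immediately discontinued from study treatment".

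Footnote c defines cholestasis as ALP above 2.0 x ULN with R below 2, where R is ALT divided by ALP, each in multiples of ULN. Section 6.5.1.1 repeats that definition. It orders immediate discontinuation unless there is cholestasis or another explanation. Its opening sentence, however, describes potential drug-induced liver injury as occurring with a normal ALP.

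Section 6.5 gives the mandatory rows their force: "Deviations to mandatory dose interruptions are not allowed". It also names Table 6-2 as the place where mandatory permanent discontinuations are indicated.

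**The concern.** A dosing table should give one action for one laboratory value. Here a drug-attributed ANC of 1.2 x 10^9/L falls in two rows with opposite instructions, one of them binding. Inclusion criterion 9 admits subjects with ANC of at least 1.0 x 10^9/L, so a value acceptable at entry could later be read as requiring a mandatory hold. A literal reader could interrupt without need and, if the value persisted, discontinue the subject. Treatment discontinuation is intercurrent event 4a in Section 12.4.2, and the primary analysis there is limited to subjects who completed 26 weeks on treatment.

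The liver row errs in the other direction. Its bracket is narrower than the definition it is meant to restate, so a site working from the cell alone could continue treatment where footnote c and Section 6.5.1.1 call for a stop. For subjects with normal baseline values the row contradicts itself: its criterion cell uses footnote c, its action cell the bracket.

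**Working it through.** There is no sample size, power or alpha figure to reproduce. The check compares printed thresholds.

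**1. Neutropenia bands (x 10^9/L, from Table 6-2).**
- Grade 2 = [1.0, 1.5). Grade 3 as printed = [0.5, 1.5). Grade 4 = below 0.5.
- Overlap of Grades 2 and 3 = [1.0, 1.5). Width 1.5 − 1.0 = 0.5, and 0.5/0.5 = 100% of Grade 2.
- With the Grade 3 upper limit at 1.0, the bands are [1.0, 1.5), [0.5, 1.0) and below 0.5: no overlap and no gap.
- In both versions every ANC below 1.0 carries a mandatory action, so the misprint leaves no low value uncovered.

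**2. Which limit was meant.** The protocol does not reproduce the CTCAE limits, so the evidence must come from the table itself. The column header and Section 8.3.2 assign the grade by CTCAE version 5, and one value cannot hold two grades. The Grade 2 floor is 1.0. The Grade 3 hold ends at Grade 2 or better, which has no clear meaning if the bands overlap. Febrile neutropenia uses 1.0. The platelet rows just below are contiguous (75–50, 50–25, below 25). All of this points to 1.0.

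**3. Liver row (ALT and ALP in multiples of ULN, R = ALT/ALP).**
- Bracket: stop if ALP < 1.
- Footnote c: stop unless ALP > 2 and R < 2. Since R < 2 means ALP > ALT/2, this is stop unless ALP > max(2, ALT/2).
- The tests disagree for ALP from 1 to max(2, ALT/2): 1.0–2.0 at ALT up to 4, 1.0–3.0 at ALT 6, and 1.0–5.0 at ALT 10.

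Illustration at ALT 6 x ULN (hypothetical values):

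| ALP | R | Bracket | Footnote c |
|---|---|---|---|
| 0.9 | 6.67 | stop | stop |
| 1.5 | 4.0 | no stop | stop |
| 2.5 | 2.4 | no stop | stop |
| 3.0 | 2.0 | no stop | stop by the definition (R < 2 not met); footnote c's own note calls R ≤ 2 cholestatic |
| 3.5 | 1.71 | no stop | no stop |

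**4. How much dosing a correction could still reach.** Amendment 3 (16-Dec-2022) states that enrollment is closed. The last infusion, Week 51 Day 1, is Day (51 − 1) x 7 + 1 = 351.
- Last subject first treated by 16-Dec-2022: + 350 days = 1-Dec-2023.
- Last subject only consented by then: + 84 + 7 further days = 1-Mar-2024.

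Delayed doses could extend either date.

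**The case against.** **The neutropenia row corrects itself.** The grade is assigned by CTCAE version 5, so the bracket only restates it. A subject with ANC of 1.0 to below 1.5 is already at Grade 2 and meets the release condition at once. This stands as mitigation and makes needless interruption less likely. It does not remove two opposite instructions, one of them binding, for the same value.

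**The liver stop is already in place.** Footnote c is attached to the word, and Section 6.5.1.1 gives the definition and the order to stop. This stands too. A reader might infer that the protocol lacks a liver stopping rule for ALP between 1 and 2 x ULN. It does not: Section 6.5.1.1 covers that range. What remains is that Section 6.5 sends sites to Table 6-2 for mandatory stops, while the cell refers to 6.5.1.1 only for further follow-up evaluations.

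**Deleting the bracket alone would create a new mismatch.** The cell has no exemption for another explanation, whereas Section 6.5.1.1 has one. Removing the bracket would extend an unconditional stop into a range where the text allows that exemption. This stands, and the fix below allows for it.

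**Exposure is small.** Table 6-2 covers adverse drug reactions only, and Section 4.5 reports from the placebo-controlled study that "there was no difference between the arms in the incidence of neutropenia or white blood cell counts". That supports a small drug-related risk but gives no absolute rate, so it cannot size the problem.

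**Conclusion.** Both thresholds are wrong as written, and the point is minor. The neutropenia misprint covers 100% of the Grade 2 band and errs towards over-interruption. The ALP bracket matters more, because it narrows a mandatory stop for a site that reads only the table.

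The analysis method, alpha and sample size do not change. It would go too far to say that the primary analysis cannot be touched, since a literal reading could cause an avoidable discontinuation (event 4a). A reader might equally infer that subjects were wrongly held, withdrawn or kept on treatment. The documents give no counts, so that inference is unsupported in either direction.

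The benefit of correcting is limited to infusions still to be given. On the nominal schedule, and assuming the last subject had at least consented by 16-Dec-2022, these end between 1-Dec-2023 and 1-Mar-2024. SAP Amendment 4 is dated 20-Feb-2024, before database lock, so little or no dosing may remain.

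**What to change.** 1. Table 6-2, neutropenia, Grade 3: change the band to ANC < 1.0 x 10^9/L to 0.5 x 10^9/L.
2. Table 6-2, combined ALT and direct bilirubin action cell: delete the bracket ALP < ULN, and make the stop apply unless there is cholestasis as defined in footnote c or another explanation, so that the cell and Section 6.5.1.1 state one rule.
3. Section 6.5.1.1, opening sentence: replace the reference to a normal ALP with the same definition of cholestasis.
4. In the same edit, settle R = 2 exactly, which the definition in footnote c excludes and its note includes.

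There is no data or sample-size cost. Section 14.1 requires a written amendment approved by the sponsor, the IRB/IEC and, where required, health authorities before implementation, so a letter to sites would not be enough. If no amendment is otherwise planned, these corrections can wait for the next one.

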### 6.5.1 Follow-up for toxicities

Subjects whose study drug treatment is interrupted or permanently discontinued due to an AE must be followed up at least once a week (or more frequently if required by institutional practices, or if clinically indicated) for 4 weeks, and subsequently at approximately 4-week intervals, until resolution or stabilization of the event, whichever comes first. Appropriate clinical experts (e.g. ophthalmologist, endocrinologist, dermatologist, psychiatrists etc.) should be consulted as deemed necessary. All subjects must be followed up for AEs and SAEs for 105 days as applicable following the last dose of study of treatment.

#### 6.5.1.1 Follow up on potential drug-induced liver injury (DILI) cases

Subjects with an elevation of transaminases in combination with an increase of total bilirubin (TBIL) and a normal ALP may be indicative of potential DILI, and should be considered as clinically important events.

**NOTE:** Subjects with SCD tend to have elevated transaminases, especially AST and indirect bilirubin, due to the hemolytic nature of their condition. Hence, ONLY ALT and direct bilirubin will be required in this criteria.

Subjects meeting any of the following criteria will require further follow-up as outlined below:

- **For subjects with normal ALT and direct bilirubin value at baseline:**  
ALT  $> 3.0 \times$  ULN combined with direct bilirubin  $> 2.0 \times$  ULN without evidence of cholestasis
- **For subjects with elevated ALT or direct bilirubin value at baseline:**  
ALT  $> 2 \times$  baseline AND direct bilirubin  $> 2 \times$  baseline
- **For subjects with normal ALT at baseline:** ALT  $> 5.0 \times$  ULN for more than 2 weeks
- **For subjects with elevated ALT at baseline:** ALT  $> 3.0 \times$  baseline for more than 2 weeks

For these subjects, repeat LFTs as soon as possible, preferably within 48-72 hours. Subjects should be closely monitored and workup for competing etiologies initiated, including hemolysis or cholestasis, defined as ALP elevation  $> 2.0 \times$  ULN with R value  $< 2$ .

Note: (The R value is calculated by dividing the ALT by the ALP, using multiples of the ULN for both values. It denotes whether the relative pattern of ALT and/or ALP elevation is due to cholestatic (R  $\leq 2$ ), hepatocellular (R  $\geq 5$ ), or mixed (R  $> 2$  and  $< 5$ ) liver injury).

In the absence of cholestasis or an alternative explanation, these subjects should be immediately discontinued from study treatment. The evaluation should include laboratory tests, detailed history, physical assessment and the possibility of new liver lesions, obstructions/compressions as described below.

1. Laboratory tests should include ALT, AST, albumin, creatine kinase, total bilirubin, direct and indirect bilirubin, gamma-glutamyl transferase (GGT), prothrombin time (PT)/INR, and ALP.
2. A detailed history, including relevant information, such as review of ethanol, concomitant medications, herbal remedies, supplement consumption, history of any pre-existing liver conditions or risk factors, should be collected.

3. Further central testing for acute hepatitis A, B, C or E infection and liver imaging (e.g. biliary tract) may be warranted.
4. Additional central testing for other hepatotropic viral infection (CMV, EBV or HSV), autoimmune hepatitis or liver biopsy may be considered as clinically indicated or after consultation with specialist/hepatologist.

All cases confirmed on repeat testing and meets the laboratory criteria defined above, with no other alternative cause for LFT abnormalities identified, should be considered as “medically significant”, thus, meet the definition of SAE and should be reported as a SAE using the term “potential drug-induced liver injury”. All events should be followed up with the outcome clearly documented.

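### For isolated ALT elevation lasting more than 2 weeks without cholestasis or another explanation, Protocol Section 6.5.1.1 says discontinue, while Table 6-2 says maintain the dose (Grade 2) or interrupt and resume (Grade 3)

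*Protocol*

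**What the plan says.** Protocol Section 6.5.1.1 gives four laboratory criteria for potential drug-induced liver injury, and any one is enough. Two rest on ALT alone:

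- normal baseline ALT: above 5.0 x ULN for more than 2 weeks;
- elevated baseline ALT: above 3.0 x baseline for more than 2 weeks.

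The section calls for repeat liver tests and a work-up for other causes, and then states: "In the absence of cholestasis or an alternative explanation, these subjects should be immediately discontinued from study treatment".

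Table 6-2 treats isolated ALT elevation by multiples of ULN only. Grade 2 (above 3.0 to 5.0 x ULN) carries "Recommendation: Maintain dose. Repeat LFTs", with weekly monitoring until ALT is at or below 3.0 x ULN if the result is confirmed. Grade 3 (above 5.0 to 20.0 x ULN) carries "Recommendation: Interrupt dose. Repeat LFTs", again with weekly monitoring to 3.0 x ULN or below, and then "If resolved, then continue with next dose scheduled". For isolated ALT, permanent discontinuation is marked mandatory only at Grade 4 (above 20.0 x ULN).

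Protocol Section 6.5 makes permanent discontinuation mandatory for the events so marked in Table 6-2. Only the combined ALT and direct bilirubin row of the table refers the reader to 6.5.1.1.

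**The concern.** Both provisions cover an ALT elevation that persists, has no bilirubin component and has no other explanation. The table rows monitor until resolution with no time limit, so they still apply after 2 weeks, when 6.5.1.1 also applies. One place then lets dosing continue or resume, and the other ends it.

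The first stake is subject safety: these are liver-related dosing rules, and two sites with the same laboratory course could act differently while each follows the protocol.

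The second is the analysis. Treatment discontinuation is intercurrent event 4a, for which data after discontinuation are set aside and imputed to Week 26 (Protocol Section 12.4.2; SAP Section 2.5.3). The primary analysis is also limited to FAS subjects who completed 26 weeks on treatment (Protocol Section 12.4.2; SAP Section 2.5.2). A discontinuation before Week 26 engages both provisions. A temporary interruption is not listed as an intercurrent event and does not by itself end treatment.

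**Working it through.** The plan has no figure to reproduce here. The check is whether the 6.5.1.1 thresholds fall inside the Table 6-2 bands.

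**Inputs**
- Section 6.5.1.1: threshold 5.0 x ULN (normal baseline) or 3.0 x baseline (elevated baseline), each for more than 2 weeks.
- Table 6-2, isolated ALT: Grade 2 above 3.0 to 5.0 x ULN; Grade 3 above 5.0 to 20.0 x ULN; Grade 4 above 20.0 x ULN.
- Inclusion criterion 8: ALT up to 3 x ULN at entry, so subjects with elevated baseline ALT can enrol.

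**Normal baseline.** The threshold of 5.0 x ULN is exactly where Grade 3 starts. Every sustained value above 5.0 and up to 20.0 x ULN is therefore Grade 3 in the table and meets the 6.5.1.1 criterion.

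**Elevated baseline.** Write baseline ALT as b x ULN, with b above 1 and at most 3. The 6.5.1.1 threshold is 3b x ULN. It reaches the top of Grade 2 when 3b = 5, so b = 5/3, about 1.67.

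| Baseline (x ULN) | Threshold 3b (x ULN) | Table 6-2 grade just above threshold | Table 6-2 action |
|---|---|---|---|
| 1.2 | 3.6 | 2 | maintain |
| 1.5 | 4.5 | 2 | maintain |
| 1.67 | 5.0 | 3 | interrupt, resume if resolved |
| 2.0 | 6.0 | 3 | interrupt, resume if resolved |
| 2.5 | 7.5 | 3 | interrupt, resume if resolved |
| 3.0 | 9.0 | 3 | interrupt, resume if resolved |

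For b below 1.67, values above 3b and up to 5.0 x ULN are Grade 2. For any elevated baseline, values above both 3b and 5.0 x ULN, up to 20.0 x ULN, are Grade 3.

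**Example.** Baseline is 1.2 x ULN and ALT stays at 4.0 x ULN for 3 weeks with no cholestasis or other cause. Since 4.0 exceeds 3.6 and 3 weeks exceeds 2, Section 6.5.1.1 says discontinue. Since 4.0 lies between 3.0 and 5.0, Table 6-2 says maintain the dose.

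**Precedence.** No sentence ranks the two passages. Section 6.5 ties mandatory permanent discontinuation to the table's own markings, and the isolated-ALT Grade 2 and 3 rows are not marked.

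**The case against.** The best defence is that 6.5.1.1 is a later and more specific step. A single ALT value does not trigger it: it needs more than 2 weeks' persistence, repeat testing, a work-up, and no cholestasis or alternative explanation. It sits under Section 6.5, and Section 9.1.1 requires discontinuation for toxicity by reference to Section 6.5. This reading is possible, but it is not written down, and the isolated-ALT rows do not lead the reader to it.

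Three narrower points stand in part:

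- In Grade 3 the table also withholds drug while ALT is unresolved, so the instructions part only if ALT later falls to 3.0 x ULN or below. Section 6.5 also discontinues a subject who misses two consecutive doses because of an adverse drug reaction, which removes some long interruptions from the conflict.
- The general note under Table 6-2 asks for repeat laboratory tests that show resolution before the scheduled dose. The Grade 2 wording must be read with that note, so it is not clearly an unconditional instruction to infuse, and the row should not be called self-contradictory. The note still does not say that the subject is discontinued.
- Protocol Section 4.5 reports no evidence of severe or drug-induced hepatotoxicity, so cases may be few.

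A reader might go further and infer that a site can follow one passage only by breaching the other. The documents do not support that. The Grade 2 and 3 rows are recommendations, and Section 6.5 says "Deviations to mandatory dose interruptions are not allowed" only of mandatory interruptions, so discontinuing under 6.5.1.1 breaches nothing.

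A reader might also infer that the dosing choice decides whether a serious adverse event is reported. It does not. That duty stands only in 6.5.1.1 and turns on confirmed laboratory criteria with no other cause.

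Nor is the combined ALT and bilirubin row a firm second conflict. It too says "subject should be immediately discontinued from study treatment" and cross-refers to 6.5.1.1. It lacks the exception for an alternative explanation, but the table is titled for adverse drug reactions. Using hepatic sequestration as the test case would be inference, because its definition contains no ALT or bilirubin criterion.

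**Conclusion.** The inconsistency is real and limited to one situation: isolated ALT elevation for more than 2 weeks, up to 20 x ULN, with no cholestasis or alternative explanation. Within it, the table's Grade 2 action (elevated baseline below about 1.67 x ULN) and Grade 3 action (normal baseline, or elevated baseline with ALT above both 3 x baseline and 5 x ULN) each differ from 6.5.1.1. The Grade 2 difference is the sharper, since the table does not withhold drug there.

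The number of subjects affected is unknown, because the documents give no frequency of sustained ALT elevation. The note in 6.5.1.1 that transaminases tend to be raised in sickle cell disease singles out AST among the transaminases, so it does not show that high ALT is common. For scale, one subject is 1/34 = 2.9% of the planned evaluable number. An effect on the efficacy result is therefore possible but not quantified; the case for correction rests mainly on safety and consistent handling. The conclusion assumes that no precedence rule exists outside the two documents. It takes no view on which instruction is clinically right.

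**What to change.** Reconcile the isolated-ALT Grade 2 and Grade 3 rows of Table 6-2 with the two ALT-only criteria of Section 6.5.1.1. Add a cross-reference in each direction and state which passage governs when both apply. The sponsor's safety physicians should decide the rule. The separate criteria for normal and elevated baseline need not be merged; the text only has to lead to one instruction in each case.

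The cost is wording in one table and one section plus a letter to sites, with no new tests or subjects. Some subjects may then be handled differently from those already managed.

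Enrolment is closed (Protocol Amendment 3). If dosing has also ended, the remaining step is to identify from the laboratory data every subject who met either ALT-only criterion and to document for each whether treatment was continued, interrupted or discontinued, and how the subject was classified for intercurrent event 4a and for completion of 26 weeks on treatment. This uses data already collected.

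### For a combined ALT and direct-bilirubin rise without cholestasis but with another identified cause, Table 6-2 makes stopping treatment mandatory and Section 6.5.1.1 does not require it

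*Protocol*

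**What the plan says.** **Table 6-2, row on combined elevations.** The row covers two groups. One is introduced by "For subjects with normal baseline ALT and direct bilirubin value" and needs ALT above 3 x ULN with direct bilirubin above 2 x ULN. The other has an elevated baseline value and needs both tests above 2 x baseline. The action is marked mandatory and applies when cholestasis is absent: "ALP < ULN), subject should be immediately discontinued from study treatment". Repeat liver tests follow, "preferably within 48 hours from awareness of the abnormal results, then with weekly monitoring". The row ends by referring to Section 6.5.1.1 for further follow-up evaluations.

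**Section 6.5.** This section gives the table its force: "Permanent treatment discontinuation is mandatory for specific events indicated as such in" Table 6-2.

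**Section 6.5.1.1.** The list opens with the same two combined criteria, the first introduced by "For subjects with normal ALT and direct bilirubin value at baseline", and adds two criteria for a sustained isolated ALT rise. For all four it says "repeat LFTs as soon as possible, preferably within 48-72 hours", with close monitoring and "workup for competing etiologies initiated, including hemolysis or cholestasis". The stopping sentence is: "In the absence of cholestasis or an alternative explanation, these subjects should be immediately discontinued from study treatment". The section then reserves its DILI-specific SAE for confirmed cases in which no other cause is found.

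**The concern.** One laboratory picture leads to two stopping rules. The table looks only at cholestasis. The liver section also looks at whether something else explains the rise, and it names hemolysis among the causes to be worked up. An investigator who finds such a cause can read 6.5.1.1 as permitting treatment to continue and Table 6-2 as forbidding it.

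Three things are at stake. Sites may handle the same mandatory liver-safety event differently. The same decision may or may not be classed as a protocol deviation, depending on which passage is taken as governing. And a stop before Week 26 is a treatment discontinuation, which is intercurrent event 4a in Protocol Section 12.4.2 and SAP Section 2.5.3, so an avoidable difference in wording would reach the handling of the primary endpoint.

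**Working it through.** The plan states no figure on this point, so the check sets the two rules side by side.

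**Inputs.** The trigger, condition and action come from the combined row of Table 6-2 and from Section 6.5.1.1. The force of the table comes from Section 6.5. The definition of cholestasis comes from footnote c of Table 6-2 (ALP above 2.0 x ULN and R below 2, where R is ALT divided by ALP, each in multiples of ULN).

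**Step 1: the trigger.** The two combined criteria are the same in both passages, so a subject who meets one meets the other.

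**Step 2: the action in each case.**

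| Case | Cholestasis | Other cause identified | Table 6-2 | Section 6.5.1.1 |
|---|---|---|---|---|
| 1 | no | no | stop | stop |
| 2 | no | yes | **stop (mandatory)** | **stop not required** |
| 3 | yes | no | stop not required | stop not required |
| 4 | yes | yes | stop not required | stop not required |

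Only case 2 differs. Cases 3 and 4 arise only with an elevated baseline, because for a normal baseline both passages already build absence of cholestasis into the criterion.

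**Step 3: an example of case 2 (values assumed for illustration).** Normal baseline, ALT 4 x ULN, direct bilirubin 2.5 x ULN, ALP 0.9 x ULN.

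- Criterion: 4 > 3 and 2.5 > 2, so it is met.
- Cholestasis: ALP is below ULN, and R = 4 / 0.9 = 4.4, which is not below 2. It is absent both by the row's parenthesis and by footnote c.
- If another cause is identified, the table row still stops treatment. The stopping sentence in 6.5.1.1 does not apply.

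**Step 4: does other text settle it?**

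- The row's reference to 6.5.1.1 covers follow-up evaluations, not the decision to stop.
- Section 6.5 makes the table's mandatory entries binding and mentions no liver exception.
- The title of Table 6-2 speaks of adverse drug reactions, which Section 6.5 explains as events attributable to study drug. The row itself is triggered by laboratory values and contains no attribution step.
- Could the sentence in 6.5.1.1 be read as requiring a stop when either cholestasis or an alternative explanation is missing? Case 2 would then agree, but case 3 would stop under 6.5.1.1 and not under the table. For normal-baseline subjects the mention of an alternative explanation would have no effect. That reading also sits badly beside the work-up for competing causes.

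The difference in case 2 therefore remains.

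**The case against.** The strongest reply is that a site can satisfy both passages by following the table. Section 6.5.1.1 exempts explained cases only by implication and does not forbid stopping. Section 6.5 gives the table priority for events it marks mandatory, and the row is more specific than a follow-up section with four triggers. This is right as far as it goes: the conflict is between a mandatory stop and no requirement to stop, not between opposite orders. But the exception in 6.5.1.1 then has no effect for the combined criterion, and nothing tells the investigator so.

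Several stronger readings do not stand:

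- *Explained rises are expected in this population.* A reader might infer this from the note on hemolysis in 6.5.1.1. The note singles out AST and indirect bilirubin, and for that reason restricts the criteria to ALT and direct bilirubin. It does not show how often an explained combined rise would occur.
- *The passages prescribe a different order of steps.* Both ask for immediate discontinuation. Section 6.5.1.1 mentions the repeat test first but does not make stopping wait for it.
- *The repeat-test intervals conflict.* Both are stated as preferences, and a repeat within 48 hours meets both.
- *An explained stop would go unreported.* Section 8.3.2 puts laboratory abnormalities that require action on study treatment on the AE page, Section 6.5.1 requires follow-up, and Protocol Section 12.6 and SAP Section 2.7.1 summarize AEs leading to discontinuation. The absence of a DILI-specific SAE when another cause is found is what 6.5.1.1 intends.
- *Every such stop removes a subject from the primary analysis.* A stop after Week 26 does not affect the 26-week set. For an earlier stop, the intercurrent-event rule imputes the remaining period. Removal would follow only from the separate statement that the primary analysis uses subjects who completed 26 weeks on treatment.

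**Conclusion.** The point holds for one case: the shared combined criterion is met, cholestasis is absent (for example, ALP below ULN), and another cause has been identified. There Table 6-2 mandates immediate discontinuation and Section 6.5.1.1 does not require it. This rests on reading the stopping sentence in 6.5.1.1 as needing both cholestasis and an alternative explanation to be absent, the only reading that fits its work-up for competing causes.

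The number of subjects affected cannot be estimated from the documents and may be zero. Enrollment is closed at 36, so the remaining value lies in consistent handling and in classifying deviations. Sample size and alpha are not affected. The passages are wrong as written and should be reconciled, but the consequence is limited.

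**What to change.** Reconcile the combined row of Table 6-2 with Section 6.5.1.1 so that both state the same discontinuation condition. Either both carry the alternative-explanation exception, stating who judges it and by when, or neither does. The sponsor decides which clinical rule applies.

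Align the advisory repeat-test interval in the same edit, so that sites work from one figure.

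The cost is a wording change in two places of the protocol. It needs no new assessment, no new safety report and no change to the SAP.
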